8.3.7 Estimated time needed for the enrolment

It is expected to enrol 20 patients within 4 months.

8.3.8 Relationship of investigation population to target population

Patients with CRS have two or more symptoms, one of which should be either nasal blockage/obstruction/congestion or nasal discharge (anterior/posterior nasal drip), lasting for 12 weeks or longer. Healsea® Chronic is indicated in adults over 18 years in the treatment of nasal symptoms of sinonasal conditions. The investigation population is thus a target population of Healsea® Chronic.

8.3.9 Vulnerable, pregnant and breastfeeding population

Patient under tutorship or guardianship are not eligible.

Pregnant and breastfeeding women are not eligible too.

8.3.10 Compensation

A compensation of 200 euros for costs resulting from participation in the clinical investigation (transportation, absence of work..) will be paid to each patient who complete the study.

8.4 Procedures

8.4.1 Study procedures

The study will comprise 2 visits and 1 telephone call.

Visit 1 (V1) – (Day 1): Screening/Inclusion

The investigator will give oral information relative to the study to the participant and answer to all the questions raised by the patient. If he/she agrees to participate in the study, he/she will be asked to sign and date a consent form.

Each screened subject will be assigned a subject identifier number during screening. The subject identifier number will contain the site number (01) and the subject number assigned in numerical order at the screening visit based on chronological order of screening dates (e.g., 01-10 for the 10th subject screened at the Site #01).

The investigator or his/her delegated designee will:

- Record demographic data and medical history and ongoing medication,
- Perform a rhinologic examination,
- Verify that eligibility criteria are fulfilled,
- Proceed with the middle meatus swab collection,
- Detail the questions of the SNOT-22 and record the patient's score,
- Record adverse events if applicable,
- Explain how to collect adverse events/incidents/expected side effects and concomitant medications for reporting at the telephone call/visit,
- Deliver Healsea® Chronic and explain to the patient how to use it.

The patient will be ask to bring back the container at the end of the treatment period.

D1-D30 (at home):

The patient will be instructed to self administer Healsea® Chronic nasal spray twice a day (1 puff, 1-2 sec) in each nostril during 30 days.

D15±3 (at home): Telephone call

The Investigator or his/her delegated designee will call the patient to review patient status and study progress, adverse events/incidents/expected side effects and concomitant treatments.

Visit 2 (V2) – (Day 30 ±5): end of treatment

The investigator or his/her delegated designee will:

- Perform a physical and clinical examination,
- Record the SNOT 22 score in the CRF,
- Proceed with the middle meatus swab collection,
- Report the adverse events/incidents/expected side effects and concomitant medications in the CRF,
- Ask the patient to complete the satisfaction questionnaire and report the result in the CRF,
- Measure compliance to Healsea® Chronic intake.

8.4.2 Permitted and forbidden concomitant medications

All concomitant medications are authorized during the investigation, except nasal irrigation, systemic corticosteroids, topical (nasal mucosa) and systemic antibiotics.

8.4.3 Exclusion period

The patients will be asked to not participate in another study during their study participation.

8.4.4 Activities performed by sponsor representatives (excluding monitoring)

The sponsor will implement and write clinical quality procedures to ensure that the clinical investigation is conducted and monitored and that data are generated, documented, recorded, evaluated and reported in compliance with the ISO 14155:2020, the CIP, any subsequent amendment(s) and any other applicable standards and in accordance with the regulatory requirements. The sponsor will ensure ongoing risk management throughout the clinical investigation and will take all measures to protect rights, safety and well-being of children who participate in the study.

The sponsor is required to report noncompliance trends and safety issues to the CA and investigators.

The sponsor shall report on the progress and status of the clinical investigation to the CA.

The sponsor will determine the frequency and type of audit to be performed. An audit can be used:

- i) As a routine part of the sponsor's quality assurance,
- ii) To assess the effectiveness of the monitoring activity,
- iii) Whenever there are serious or repeated CIP deviations or suspicion of fraud,
- iv) To bring an investigation site into "inspection readiness" (i.e. to prepare the investigation site for a potential regulatory inspection),

v) When requested or suggested by a regulatory authority.

8.4.5 Any known/foreseeable factors that can compromise the outcome of the clinical investigation and methods for addressing these factors

No known or foreseeable factors that can compromise the outcome of the clinical investigation is anticipated.

8.4.6 Follow-up and medical care after completion of the study

Neither follow-up nor specific medical care for patients are foreseen after the completion of the study. Nevertheless, routine care for CRS will be provided to the patients.

8.4.7 Potential use of samples obtained from subjects

Patients' samples will be used to assess sino-nasal microbiota through 16S RNA gene amplicon sequencing only as per approved protocol.

8.5 Monitoring plan

A risk-based monitoring plan included in a separate document will describe in detail who will conduct the monitoring, at what frequency monitoring will be done, at which level of detail monitoring will be performed, and the distribution of monitoring reports. Results of the risk assessment will be used to develop a risk-based monitoring plan and a supporting rationale.

8.5.1 Initiation visit

The study will only start at a site after:

- The Ethics Committee has granted approval for the conduct of the study,
- ANSM approval,
- Essential documents are in place, such as CVs of the Investigators and site staff, and the Clinical Trial Agreement signed.

In agreeing to participate, the investigator undertakes to strictly comply with the study protocol, Good Clinical Practice, the French regulation and to MDR. The investigator also guarantees the authenticity of the data collected in the context of the study and agrees to the legal provisions for study sponsor quality control.

8.5.2 Monitoring

Study monitoring under responsibility of Lallemand Pharma by qualified staff will be performed at various stages of the study. Monitoring will include on-site visits and centralized data review to assure that the investigation is conducted according to the CIP and comply with applicable regulations and deadlines. On-site review of Case Report Form (paper CRFs) will include the review of forms for completeness, clarity and consistency with source documents available for each subject. In case of queries, the investigator should respond within agreed timelines.

The investigator must permit study-related monitoring visits, audits review by the Ethic Committee and ANSM, and allow direct access to source data and source documents provided that subject confidentiality is protected. In case of an audit appointed by Lallemand Pharma, the investigator will receive written notification in advance.

9. Statistical design and analysis

Patients and disease characteristics will be described at baseline.

16S rRNA Gene Sequence Analysis

The normal distribution of the values is verified thanks to normality tests (e.g. Shapiro-Wilk test). However, it is most likely that the group size will be insufficient to apply parametric statistical tests. Significant variations in total number of bacterial 16S rRNA gene copies or in alpha diversity are assessed using the Kruskal-Wallis test or the Wilcoxon rank-sum test. Multidimensional scaling analyses (MDS) are performed on beta diversity distances matrices and differences between groups were assessed using PERMANOVA and PERMDISP analyses (2000 permutations). LEfSe (Linear discriminant analysis Effect Size) analyses, based on non-parametric tests are used to determine significant variations in taxa relative abundance [17].

Secondary endpoints

Values and changes from baseline to D30/end of study of the SNOT-22 total score will be described.

Patients satisfaction will be described at D30/end of study.

Safety

All adverse events/incidents/expected side effects will be listed, but only treatment-emergent adverse events/incidents (non-serious + serious) and expected side effects will be summarized by the number and percentage of patients, classified by System Organ Class and Preferred Term as defined by MedDRA dictionary.

Frequency and percentage of patients with at least one reported adverse event/incident/expected side effect will be tabulated by System Organ Class.

10. Data collection

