8.1 General

8.1.1 Design type of clinical investigation

This is an exploratory study, open label in one site, in France. No control group is deemed necessary at this stage.

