8.1.3 Primary Endpoint

Modifications in microbial load and/or profile

To determine the impact of Healsea® Chronic on the nasal microbiome, the microbial load will be evaluated by quantitative PCR and the microbiome taxonomic profiling by 16S rRNA gene sequencing. Data collected in patients before and after 1 month-treatment with Healsea® Chronic will be compared using statistical analyses to assess changes in microbial species abundance and diversity. Furthermore, special attention will be given to typical sino-nasal pathogens (e.g. *Staphylococcus aureus*, *Streptococcus pneumoniae*, *Haemophilus influenzae*, *Moraxella catarrhalis*) at genus level, and if reachable at species level.

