8.1.5 Methods and timing for assessing, recording and analysing variables

8.1.5.1 Middle meatus swab specimen

Collection of middle meatus swab specimens will be performed at V1 and V2. A sterile stick swab (reference MW940; Medical Wire) will be introduced deeply within the middle meatus rotated at least 5 turns until visibly saturated. Immediately after collection, the swab will be placed in a dry tube (reference 62 554502; Sarstedt) and immediately stored in a freezer at -20°C.

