8.1.7 Any procedures for the replacement of subjects

No replacement of subjects is planned.

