3. STUDY DESIGN

This is a non-randomized, exploratory, monocentric, open label single-arm interventional study on medical device (PMCF investigation for medical device (MD) CE marked and used in its intended purpose with invasive and/or burdensome procedure as per Medical Device Regulation (MDR) Art. 74(1))

Investigational plan description (see Figure 1):

- Visit 1 (V1) – (Day 1): Screening/Inclusion
- Telephone call 1 (TC1) – (Day 15±3)
- Visit 2 (V2) – (Day 30±5): end of treatment

The maximal study duration for each subject is 35 days.

Visit name	Screening/Inclusion	At home	Telephone call	At home	End of Treatment
Visit Number	V1		TC1		V2
Days/Weeks	D1	D1 – D15± 3	D15±3	D15± 3 – D30± 5	D30 ± 5
Screening and General Assessments					
Patient information and Consent collection	X				
Eligibility criteria	X				
Demography and Medical history	X				
Physical and clinical examination	X				X
Ongoing medication	X				
Treatment					
Healsea® Chronic		X		X	
Assessments					
SNOT 22	X				X
Collection of middle meatus swab specimens	X				X
Adverse Events/Incidents and concomitant medication reporting	X		X		X
Satisfaction questionnaire					X
Compliance to study product					X

Figure 1 : Flow chart of the study

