5. DEFINITION OF THE ANALYSIS SETS

Screened subjects: all subjects who signed an informed consent

Included subjects: all screened subjects who will have been expected to participate in the study.

Safety Set: all subjects who will have used the investigational medical device at least once.

Full Analysis Set (FAS): all subjects from the Safety Set who will have at least one post baseline Sino Nasal Outcome Test-22 (SNOT-22) evaluation.

Per Protocol Set (PP): all subjects from the FAS without any major protocol deviation.

The status of protocol deviations (minor or major) will be validated during the data review meeting.

Any subject not satisfying major entry criteria or for whom post inclusion data are not available will be identified by the Validation Committee during the data review, and could be excluded from the FAS Set in agreement with circumstances exposed in the ICH-E9 §5.2.1.

Safety analysis will be performed on the Safety Set.

Efficacy analysis (except primary efficacy criterion) will be performed on the FAS.

Note: primary efficacy criterion (16S rRNA gene high throughput sequencing) will be analysed separately by a dedicated team specialized in microbiome analysis.

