6.3. Statistical/Analytical issues

6.3.1. Significance level

All statistical analyses will be performed at the 0.05 global significance level (type I error rate), using two-sided tests.

Because of the exploratory nature of the study, all the statistical results have to be considered within a descriptive perspective and not as inferential issues. No adjustment for Type I error is done. P-values of statistical tests will be provided for information only.

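### The plan names independent-sample rank tests (Kruskal-Wallis or rank-sum) for 16S copy number and alpha diversity, but the only comparison is before against after in the same patients

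*Protocol*

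**What the plan says.** - **Test.** In Protocol section 9, under 16S rRNA Gene Sequence Analysis, variations in total 16S copies or "in alpha diversity are assessed using the Kruskal-Wallis test or the Wilcoxon rank-sum test". The synopsis says the same. Normality is to be checked first, but the plan expects the group size to be too small for parametric tests.
- **Design.** Protocol 8.1.1: "No control group is deemed necessary at this stage". SAP section 3: "This is a non-randomized, exploratory, monocentric, open label single-arm interventional study on medical device".
- **Sampling.** Protocol 8.1.5.1: "Collection of middle meatus swab specimens will be performed at V1 and V2".
- **Comparison.** Protocol 8.1.3: "Data collected in patients before and after 1 month-treatment with Healsea® Chronic will be compared using statistical analyses".
- **Sample size.** 20 patients, called arbitrary (Protocol 8.3.6, SAP section 4). Protocol 7.4 sets no effect size.
- **Where the primary analysis sits.** SAP section 5 says that it "will be analysed separately by a dedicated team specialized in microbiome analysis". SAP 10.1 refers to a separate document for the method and names no test.
- **Status of p-values.** SAP 6.3.1 sets a two-sided 0.05 level, but adds: "P-values of statistical tests will be provided for information only".

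**The concern.** The rank-sum test takes its null distribution from two independent groups. Kruskal-Wallis with two groups is the same test apart from the continuity correction, so offering one or the other provides no paired option. No subgroup or other independent-group comparison of microbiome data is defined anywhere. The named tests can therefore only be meant for V2 against V1, where every patient contributes to both sides.

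If some patients have consistently higher load or diversity than others, their two values are positively correlated. The unpaired test then sets the change against the full between-patient spread and ignores the pairing. Its p-value comes out too large, and a real change may be reported as none. This bears on the study's own hypothesis about diversity (Protocol 7.1). It also bears on the stated next step: Protocol 6.6 says an observed improvement could justify a study in a larger population.

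**Working it through.** The plan gives no power, SD or effect size, so there is no stated figure to reproduce. What can be computed is how the named test behaves on paired data.

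**Inputs from the documents:** 20 patients, hence 20 pairs; two-sided 0.05.

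**Assumptions, because the documents give no values:** within-patient correlation ρ from 0 to 0.7; a shift of 0.5 or 0.8 SD at V2.

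**Normal approximation.** With SD σ at each visit and n pairs, the mean change has variance 2σ²(1−ρ)/n. An unpaired test uses 2σ²/n. Its true type I error is therefore

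2 × [1 − Φ(1.96 / √(1−ρ))].

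- ρ = 0.3: 1.96/√0.7 = 2.34, giving 1.9%
- ρ = 0.5: 1.96/√0.5 = 2.77, giving 0.6%
- ρ = 0.7: 1.96/√0.3 = 3.58, giving 0.03%

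The shift detectable with 80% power at ρ = 0.5, in SD units:

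- Paired: (1.96 + 0.84) × √(2 × 0.5/20) = 0.63
- Unpaired: 1.96 × √(2/20) + 0.84 × √(2 × 0.5/20) = 0.81

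**Simulation of the actual tests.** 20,000 data sets per cell (Monte Carlo SE at most 0.4 points); bivariate normal pairs, SD 1 at each visit; rank-sum by its normal approximation, signed-rank by its exact null distribution. All entries are percentages.

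| ρ | 0 | 0.1 | 0.3 | 0.5 | 0.7 |
|---|---|---|---|---|---|
| Type I error, rank-sum | 5.0 | 4.1 | 2.2 | 0.8 | 0.2 |
| Power at 0.5 SD, rank-sum | 32 | 31 | 30 | 27 | 24 |
| Power at 0.5 SD, signed-rank | 31 | 33 | 42 | 54 | 76 |
| Power at 0.8 SD, rank-sum | 67 | 68 | 70 | 72 | 77 |
| Power at 0.8 SD, signed-rank | 65 | 69 | 80 | 91 | 99 |

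The signed-rank type I error stays between 4.7% and 5.2%.

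**Non-normal data.** With heavy-tailed (t with 3 df) or skewed (exponential) margins, the rank-sum type I error is within 0.2 points of the row above. Power depends much more on the shape. The signed-rank test has the higher power only above a correlation of about 0.05 (normal), 0.25–0.4 (heavy-tailed) or 0.4–0.5 (skewed). Below those values it loses up to 2, 9 and 17 points respectively. For skewed data at ρ = 0.5 and a 0.5 SD shift, power is 62% (rank-sum) against 67% (signed-rank).

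**Incomplete pairs.** Take 20 V1 swabs but only 16 usable V2 swabs, normal data, 0.5 SD shift, same five correlations. Rank-sum on all swabs has power 28/28/26/23/20%; signed-rank on the 16 pairs has 24/26/33/43/64%.

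**Scale of the copy counts.** The signed-rank test depends on the measurement scale, whereas rank-sum does not. For lognormal copies with a 0.5 SD shift on the log scale and ρ = 0.5, signed-rank power is about 55% on log10. On raw copies it is 47% (log10 SD 0.5) or 43% (log10 SD 1.0).

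**The case against.** **The governing method is not visible.** The SAP hands the primary analysis to a specialist team and a separate document, which may well specify a paired test. This stands as a limit. The finding concerns what the protocol states, not what was eventually run. But the SAP neither withdraws nor corrects the protocol sentence, which remains the only stated rule for the primary endpoint.

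**The consequence is modest.** The study is exploratory, p-values carry no decision, and with positive correlation the error is conservative, so it produces no excess of false positives. This also stands, and it limits the severity. The p-values will still be reported, however, and a test with a true error rate near 1% can suggest no change where there is one.

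**The power gain is not universal.** It needs a correlation that the documents do not give, and normal data are the most favourable case. For skewed data, a 0.8 SD shift and ρ = 0.5, power is 92.5% against 92.9%, which is no real difference. At ρ = 0.3 the rank-sum test is ahead, 90.6% against 86.1%. This is correct, so the argument should not rest on power alone. Calibration is the firmer ground: the rank-sum error rate is distorted under all three distributions, although only slightly at a correlation of 0.1 (4.1%), while the signed-rank test holds its level throughout.

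**Pairing may be harder than it looks.** Protocol 15.2 sends coded samples to the laboratory and withholds the decoding index. If the codes do not link visits, a paired analysis there needs an extra data-handling step. This is a fair point and is taken into the fix.

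**Conclusion.** The concern holds. The tests named in section 9 and the synopsis do not fit a single-arm before-after comparison, and nothing in the protocol or SAP corrects them. At an assumed correlation of 0.5 with 20 pairs, the nominal 5% test works at about 0.8%, and its power for a 0.5 SD shift in normal data is half that of the paired test (27% against 54%). The size depends on correlation, shift and distribution, all of which are assumed. At zero correlation both tests hold their level and the choice makes little difference for normal data.

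This should be fixed, because it concerns the primary endpoint and costs little. It does not threaten a decision. Confidence is high that the protocol text is wrong as written; whether the analysis actually run was unpaired cannot be told from these documents. For PERMANOVA, PERMDISP and LEfSe the text is only silent on pairing, and no error is claimed there.

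**What to change.** 1. In the separate microbiome analysis document, or as a documented change to the analysis, replace the named tests with the Wilcoxon signed-rank test on within-patient V2−V1 differences, for 16S copies on the log10 scale and for each alpha-diversity index. Apply the normality check to those differences.
2. Report the number of complete pairs and state how a patient with only one usable swab is handled.
3. Confirm that the sample codes link V1 and V2 of the same patient without revealing identity, or have the paired analysis run where the link is held.
4. If the 16S results are already known, report the protocol's test beside the paired test and give the reason for the change.
5. Correct section 9 and the synopsis if they can still be amended. SAP section 12 shows that data review had already taken place, so an amendment may come too late and is not essential.

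Optional, in the same document: restrict PERMANOVA permutations to within patient, and say how PERMDISP and the taxa analysis treat the pairs.

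**Cost.** A few lines of text and code, plus a linkage step if the codes do not already provide it; no extra patients or procedures. A patient with one usable swab drops out of the paired test, and Protocol 8.1.7 states "No replacement of subjects is planned". If the correlation is in fact zero, the paired test gives up 1–2 points of power for normal data and up to 9 (heavy-tailed) or 17 (skewed) points otherwise.

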Although clinical evidence from well-designed trials is scarce, European guidelines for chronic rhinosinusitis recommend daily nasal saline irrigation for reduction of the severity of symptoms of CRS [1]. A recent Cochrane analysis has concluded that daily nasal irrigation with hypertonic saline solution is more effective than placebo to improve patient symptoms [8]. The exact mechanisms by which nasal irrigation works are not known. However, most of the experts agree that it is primarily a mechanical intervention leading to direct cleansing of the nasal mucosa. Nevertheless, the efficacy of such solution remains moderate.

Healsea® Chronic is a CE marked medical device indicated in adults for the treatment of nasal symptoms of chronic rhinosinusitis. This is a seawater-based nasal spray supplemented with a natural Symbiofilm® extract (0.02%) isolated from marine bacteria. The nasal solution is hypertonic (NaCl 2.2%). Symbiofilm® is a marine postbiotic comprising active exopolysaccharides with emulsifying properties and *in vitro* antibiofilm activity. Antibiofilm properties have been demonstrated with the colorimetric microtiter plate assay [9]. In this model, a significant inhibition of *Staphylococcus aureus* and *Haemophilus influenzae* biofilms are observed. Detachment properties from human nasal epithelial cells of *Staphylococcus aureus* and *Pseudomonas aeruginosa* has also been demonstrated *in vitro*, suggesting an inhibition of biofilm formation at early stage in this model. Symbiofilm® has no bacteriostatic nor bactericidal activities.

To date, properly designed study to evaluate for the effect of topical therapies on microbiome are scarce so no definite conclusion can be made. In one study, use of saline irrigation with or without budesonide^{DCI} used was not associated with significantly distinct microbiota composition among either controls or post-operative CRS with polyp patients [10].

We design this exploratory study aiming at determining if the antibiofilm properties of Symbiofilm may modify sino-nasal microbiota, impacting α and/or β diversities. To this end middle meatus swab specimen will be taken from CRS patients before and after treatment with Healsea® Chronic. Bacteria colonization will be assessed using quantitative PCR and 16S rRNA gene sequencing.

6. Risks and Benefits of the Investigational Device and Clinical Investigation

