8.1.5.3 Assessment of sino-nasal microbial communities by 16S rRNA gene amplicon sequencing

DNA extraction

Genomic DNA (gDNA) is extracted using an optimized tissue-specific technique as previously described [14], [15]. This technique was carefully designed to maximize the recovery of bacterial DNA and to minimize any risk of contamination from the environment and the reagents. The quality and quantity of extracted gDNA are monitored by gel electrophoresis (1% w/w agarose in 0.5× TBE buffer) and NanoDrop 2000 UV spectrophotometer (ThermoFisher Scientific). All gDNA samples are stored at -20 °C until further processing.

Bacterial quantification by quantitative PCR (qPCR)

Total number of bacterial 16S rRNA gene copies is evaluated by real-time PCR amplification targeting the hypervariable regions V3-V4 with the primers: EUBF 5'-TCCTACGGGAGGCAGCAGT-3' and EUBR 5'-GGACTACCAGGGTATCTAACCTGTT-3'. The qPCR is realized in triplicate on a ViiA 7 PCR system (Life Technologies) using SYBR Green technology and the specificity of all qPCR products is assessed by systematic analysis of a post-PCR dissociation curve performed between 60°C and 95°C. The absolute number of copies of the 16S rRNA gene is determined by comparison with a quantitative standard curve generated by serial dilution of linearized plasmid standards.

Bacterial 16S rRNA gene sequencing

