The V3-V4 hypervariable regions of the 16S rRNA gene are amplified by PCR using universal primer Vaiomer 1F (CTTCCCTACACGACGCTTCCGATCT-TCCTACGGGAGGCAGCAGT, partial P5 adapter-primer) and universal primer Vaiomer 1R (GGAGTTCAGACGTGTGCTTCCGATCT-GGACTACCAGGGTATCTAACCTGTT, partial P7 adapter-primer), which are fusion primers based on the qPCR primers with sequencing adapters. The first PCR reaction is carried out on a Veriti Thermal Cycler (Life Technologies) as follows: an initial denaturation step (94°C for 10 min), 35 cycles of amplification (94°C for 1 min, 68°C for 1 min and 72°C for 1 min) and a final elongation step at 72°C for 10 min. Amplicons (467 bp on the Escherichia coli reference genome) are then purified using the magnetic beads CleanNGS for DNA clean-up (CleanNA). A second PCR reaction for sample multiplexing is performed using tailor-made 6-bp unique index sequences with the forward primer Vaiomer 2F (AATGATA CGCG ACCACGAGATCTACACT-CTTCCCTACACGAC, partial P5 adapter-primer targeting primer 1F) and reverse primer Vaiomer 2R (CAAGCAGAAGACGGCATACGAGAT-index-GTGACT-GGAGTTCAGACGTGT, partial P7 adapter including index-primer targeting primer 1R). This second PCR step is run as follows: an initial denaturation step (94°C for 10 min), 12 cycles of amplification (94°C for 1 min, 65°C for 1 min and 72°C for 1 min) and a final elongation step at 72°C for 10 min. Amplicons are purified as described for the first PCR round. All libraries are pooled in the same quantity to generate an equivalent number of raw reads and are sequenced on a MiSeq Illumina platform (2 x 300 bp paired-end MiSeq kit v3, Illumina).

16S rRNA Gene Sequence Analysis

The targeted metagenomic sequences are analyzed using a bioinformatics pipeline based on 'find, rapidly, OTUs with Galaxy solution' (FROGS) guidelines [16]. In brief, after demultiplexing of barcoded Illumina paired reads, single-read sequences were cleaned and paired into longer fragments. OTUs are produced with single-linkage clustering. The taxonomic assignment is performed by BLAST against SILVA database to determine bacterial profiles from phylum to genus, and when reachable to species level. The following filters are applied: amplicons with a length of <350 nt or a length of

>490 nt are removed and OTUs with abundance lower than 0.005% and that appear less than twice in the entire dataset are removed. Alpha and beta diversity analyses are conducted on the OTU table.

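### The only taxon-level method named works on relative abundance and is never combined with the total 16S copies measured on the same swab, so a taxon's rise or fall cannot be read from it alone

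*Protocol*

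**What the plan says.** Protocol section 8.1.3 defines the primary endpoint as "Modifications in microbial load and/or profile". It says that data from before and after treatment "will be compared using statistical analyses to assess changes in microbial species abundance and diversity", without stating whether abundance is relative or absolute. It adds that "special attention will be given to typical sino-nasal pathogens", with four species as examples, at genus level and at species level where possible. No test and no scale is given for them.

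Section 8.1.5.3 describes two measurements on each swab:

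- **qPCR, in triplicate.** "The absolute number of copies of the 16S rRNA gene is determined by comparison with a quantitative standard curve".
- **Sequencing.** "All libraries are pooled in the same quantity to generate an equivalent number of raw reads". The read count of a swab therefore carries no information on its bacterial load; sequencing alone gives proportions.

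Section 9 analyses these separately. For load and alpha diversity: "Significant variations in total number of bacterial 16S rRNA gene copies or in alpha diversity are assessed using the Kruskal-Wallis test or the Wilcoxon rank-sum". For beta diversity it names PERMANOVA and PERMDISP. For taxa, LEfSe analyses "are used to determine significant variations in taxa relative abundance". That is the only taxon-level method named.

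SAP sections 5 and 10.1 leave the primary analysis to a specialist team and a separate document, which is not among those supplied. SAP section 6.3.1 makes all p-values informative only.

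**The concern.** Removal of bacteria is a plausible effect of this device. Protocol section 5 says of nasal irrigation that "most of the experts agree that it is primarily a mechanical intervention leading to direct cleansing of the nasal mucosa", and describes the added extract as detaching bacteria in vitro without killing them. Sections 6.6 and 7.1 look to the swabs for a first view of the mechanism in vivo, and section 6.6 says that an improved microbiota could justify larger studies.

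A proportion cannot separate a fall in one taxon from a rise in the others, and it does not move when all taxa fall together. If the pathogen results are read from relative abundance alone, a pathogen that was cleared along with everything else would be reported as unchanged, and one that did not change could be reported as increased.

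**Working it through.** **Inputs.** From the documents: 20 patients, one swab before and one after; two-sided 0.05; rank-sum named for load; LEfSe on relative abundance named for taxa. The documents give no effect size, standard deviation or taxon share, so these are assumed below. The sample size is called arbitrary, so the plan has no figure to reproduce.

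**1. Even fall (exact).** Take three taxa with 100,000, 300,000 and 600,000 copies, 1,000,000 in total. The shares are 10%, 30% and 60%. After a tenfold fall the copies are 10,000, 30,000 and 60,000, and the shares are still 10%, 30% and 60%. Total copies go from 1,000,000 to 100,000. The taxon analysis has nothing to detect; the load analysis does.

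**2. Unchanged taxon (exact).** If a taxon has baseline share p and does not change while all others are multiplied by k, its new share is p / (p + (1 - p)k).

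| Baseline share | Others halved (k = 0.5) | Others down tenfold (k = 0.1) |
|---|---|---|
| 5% | 0.05/0.525 = 9.5% (x1.90) | 0.05/0.145 = 34.5% (x6.90) |
| 10% | 0.10/0.55 = 18.2% (x1.82) | 0.10/0.19 = 52.6% (x5.26) |
| 50% | 0.50/0.75 = 66.7% (x1.33) | 0.50/0.55 = 90.9% (x1.82) |

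**3. Share x total copies.** In the last cell the total falls to 0.55 of baseline, and 0.909 x 0.55 = 0.50 of the original total, which is the true, unchanged amount. In step 1, 10% x 100,000 = 10,000 against 10% x 1,000,000 = 100,000, so the tenfold fall is recovered.

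**4. Rejection rates with 20 pairs (simulation, 1,500 runs per row).** A single-taxon rank test stands in for the taxon analysis; LEfSe was not run. Assumptions: taxon share 10%; between-patient SD of log10 load 0.5 with swab-yield SD 0.2 per visit (case A), or 0.8 with 0.4 (case B); between-patient taxon SD 0.3; visit-level noise of 0.2 for the taxon and 0.05 for the rest, all in log10. Each cell gives rank-sum / signed-rank.

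| Scenario | Relative abundance | Total copies | Share x copies |
|---|---|---|---|
| All halved, A | 0.3% / 5.4% | 30.7% / 98.6% | 15.0% / 86.6% |
| All halved, B | 0.2% / 4.5% | 4.7% / 58.0% | 3.8% / 51.1% |
| All down tenfold, A | 0.2% / 5.2% | 100% / 100% | 100% / 100% |
| All down tenfold, B | 0.3% / 5.7% | 99.5% / 100% | 97.7% / 100% |
| Taxon unchanged, others halved, A | 78.9% / 98.5% | 14.8% / 94.5% | 0% / 5.3% |
| Taxon unchanged, others halved, B | 79.4% / 98.5% | 2.7% / 44.8% | 0.1% / 5.2% |
| Taxon unchanged, others down tenfold, A | 100% / 100% | 99.9% / 100% | 0% / 4.1% |
| Taxon unchanged, others down tenfold, B | 100% / 100% | 75.9% / 99.7% | 0.1% / 4.8% |

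The low rank-sum rates arise because that test ignores the pairing, which is a separate matter.

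**5. Sensitivity to the set-up.** With ten taxa, one dominant, within-patient log SD 1 and only the dominant taxon down 80%, an unchanged taxon was flagged on relative abundance in 30% to 37% of runs by signed-rank, 7% to 9% by rank-sum, and 6% in a variant with greater variance at V2. In the same set-up with all taxa down 80%, the planned rank-sum test on total copies rejected in 100% of runs.

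**6. Swab yield.** Section 8.1.5.1 gives no normaliser for the amount of material collected. If V2 recovery is multiplied by r with no biological change, every taxon load is multiplied by r while shares stay put. With an assumed yield log SD of 0.5, signed-rank on the dominant taxon's load wrongly flagged a change in about 23% to 27% of runs for 30% lower recovery and about 68% to 71% for half, against about 5% on relative abundance.

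**The case against.** A reader might infer that a device clearing bacteria evenly would look inactive in this study. The documents do not support that: load is the first item in the primary endpoint and is tested in the same paragraph as the taxa. An even fall can show there, depending on its size; it is lost only in the taxon-level results. The load test is also not a dependable warning for those results. When the others halve, rank-sum on total copies rejects in 2.7% to 14.8% of runs while the taxon's false rise is flagged in about 79%.

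A reader might also infer that the named pathogens will be tested only as relative abundance. No test or scale is written for them; LEfSe is simply the only taxon method listed. The separate analysis document may already use absolute abundance, and that cannot be checked.

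The mechanism argument has limits. The hypothesis in section 7.1 is a change in alpha or beta diversity, and section 5 says that lower diversity, more than higher load, characterises the disease. A fall in each pathogen's load is plausible, but it is not the stated expectation.

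The strongest objection is to taxon load as a replacement. Swab yield is not normalised, and a product meant to cleanse and decongest could alter recovery at V2. Step 6 shows that this would trade one bias for another. The objection stands, and it rules out claiming changes from taxon load alone.

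Finally, the study is exploratory and the multiplication could be done afterwards from stored data. That lowers the stakes, but a readout chosen after the results are seen carries less weight.

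**Conclusion.** The point holds for the supplied documents. The only taxon-level method named uses relative abundance, and total copies are tested separately and never combined with it. Two consequences are exact and need no assumptions: an even fall leaves every share unchanged, and an unchanged taxon's share rises when others fall (50% to 91% if the other half falls by 90%).

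How often this would mislead is not settled. Across the set-ups tried, an unchanged taxon was flagged in 6% to 100% of runs, depending on the test, the variances and the size of the fall in the other taxa. None of these figures is for LEfSe.

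With p-values for information only, the issue concerns how taxon results are interpreted, not a confirmatory conclusion. It is a cheap improvement.

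**What to change.** In Protocol section 9 and in the separate microbiome analysis document:

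- For the named pathogen genera, and species where reachable, pre-specify the within-patient V1 to V2 change in log10(relative abundance x total 16S copies).
- Report it beside the relative-abundance/LEfSe result and the change in total copies.
- Describe a taxon as risen or fallen only after reading all three together.
- State in advance how swabs in which the genus is not detected enter the log scale.

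No new sample or assay is needed. The cost is one multiplication per taxon and swab and one extra table. The two swabs of a patient must be matchable; since section 15.2 withholds the decoding index from the laboratory, the sample codes must allow this or the calculation must be done where the key is held.

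Three limits should be stated with the results. The product carries qPCR error. It also carries any difference in swab yield between visits, for which no normaliser is planned. The 16S copy number per genome cancels in a within-patient change for one species, but not fully for a genus whose species mix shifts.
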